12.2.1.1.1. Application site irritation scores

[REDACTED]

[REDACTED]

[REDACTED]

12.2.1.1.2. Pregnancy

If a patient or partner of a patient becomes pregnant during or after exposure to the trial drug (within three months of trial drug discontinuation) received in this study, the Investigator will immediately discontinue the patient from the study (if patient is still on study) and contact the Sponsor or designee. The Investigator will complete the Sponsor's (or designee's) Clinical Pregnancy Notification Form and alert the Sponsor within two days of learning of the pregnancy. Diligent efforts will be made to determine the outcome for all pregnancy exposures in the clinical trial. Information on the status of the mother and the child will be forwarded to the Sponsor.

Generally, follow-up will occur within six to eight weeks following the estimated delivery date. Any premature termination of the pregnancy will be reported. Both maternal and paternal exposure will be collected. For exposure involving the female partner of a male patient, the necessary information must be collected from the patient, while respecting the confidentiality of the partner.

Pregnancy itself is not regarded as an AE unless there is a suspicion that an investigational product may have interfered with the effectiveness of a contraceptive medication.

The outcome of all pregnancies (spontaneous miscarriage, elective termination, normal birth or congenital abnormality) must be followed up and documented even though the patient was discontinued from the study.

All reports of congenital abnormalities/birth defects are SAEs. Spontaneous miscarriages should also be reported and handled as SAEs. Elective abortions without complications should not be handled as AEs. The date of onset of the adverse event will be collected. Also, the date of the resolution of the adverse event will be collected.

12.2.1.2. Serious Adverse Event (SAE)

Any adverse event that results in one or more of the following is considered an SAE.

1. Death
2. Life Threatening - The patient was at risk of death at the time of the event. It does not refer to the hypothetical risk of death if the adverse event were more severe or were to progress
3. In-patient hospitalization (admission or prolongation of existing hospitalization). Planned hospitalizations to treat a pre-existing condition or an inpatient stay required by the protocol is not considered to be an SAE unless otherwise specified in the study protocol. If there is any doubt whether the hospitalization constitutes an SAE, it should be treated as serious and reported to the Sponsor.
4. Persistent or significant disability / incapacity - Any AE having an outcome that is associated with a substantial disruption of the ability to carry out normal life functions. This includes the inability to work. This is not intended to include transient interruptions of daily activities.
5. Congenital abnormality or birth defect - Any structural abnormality in patient offspring that occurs after intrauterine exposure to treatment.
6. Other Medically Important Events - Important medical events that may not result in death, be life-threatening, or require hospitalization may be considered a serious adverse event when, based upon medical judgement, they may jeopardize the patient or may require intervention to prevent one of the outcomes listed above.

12.2.1.3. Other Adverse Event (OAE)

OAEs will be identified by the study Medical Monitor during the evaluation of safety data for the Clinical Study Report. Significant adverse events of particular clinical importance, other than SAEs and those AEs leading to discontinuation of the patient from the study, will be classified as OAEs. For each OAE, a narrative may be written and included in the Clinical Study Report.

12.3. Recording Adverse Events

Adverse events spontaneously reported by the patient/parent/caregiver and/or in response to an open question from the study personnel or revealed by observation will be recorded during the study at the investigational site. Clinically significant changes as judged by the Investigator in laboratory values, blood pressure, and pulse will be reported as AEs. Abnormal values that constitute an SAE or lead to discontinuation of administration of trial drug must be reported and

recorded as an AE/SAE. Information about AEs/SAEs will be collected from the signing of the ICF until the last Telephone Follow-Up call. The AE term should be reported in standard medical terminology when possible.

For each AE, the Investigator will evaluate and report the onset date, resolution date, intensity, causality, action taken, serious outcome (if applicable), and whether or not it caused the patient to discontinue the study.

The relationship of the adverse event to the trial drug will be assessed using the following definitions:

- Related (An adverse event has a strong temporal relationship to trial drug or recurs on re-challenge, and another etiology is unlikely).
- Not Related (An adverse event is due to underlying or concurrent illness or effect of another drug and is not related to the trial drug (e.g., has no temporal relationship to trial drug or has a much more likely alternative etiology). The alternative etiology will be recorded in the CRF.

Intensity will be assessed according to the following scale:

- Mild (awareness of sign or symptom, but easily tolerated)
- Moderate (discomfort sufficient to cause interference with normal activities)
- Severe (incapacitating, with inability to perform normal activities)

It is important to distinguish between serious and severe AEs. Severity is a measure of intensity whereas seriousness is defined by the criteria under Section 12.2.1.2. An AE of severe intensity may not be considered serious.

Should a pregnancy occur, it must be reported and recorded on the Sponsor's (or designee's) pregnancy form. Pregnancy itself is not regarded as an AE unless there is a suspicion that an investigational product may have interfered with the effectiveness of a contraceptive medication.

The outcome of all pregnancies (spontaneous miscarriage, elective termination, normal birth or congenital abnormality) must be followed up and documented even though the patient was discontinued from the study.

All reports of congenital abnormalities/birth defects are SAEs. Spontaneous miscarriages should also be reported and handled as SAEs. Elective abortions without complications should not be handled as AEs.

12.4. Reporting Adverse Events

If any protocol defined expedited event, or serious AE occurs whether related to trial drug or not, the Investigator must notify the Sponsor within 24 hours by telephone or email.

24 Hour SAE Telephone: [REDACTED]

Email: [REDACTED]

All SAEs (related and unrelated) will be recorded from the signing of the ICF until the last Telephone Follow-Up call. Any SAEs considered related to the investigational product and discovered by the Investigator at any time after the study should be reported. All SAEs must be

reported to Zynerva within one business day of the first awareness of the event. The Investigator must complete, sign and date the SAE form, verify the accuracy of the information recorded on the SAE form with the corresponding source documents, and send a copy by e-mail to Zynerva.

Additional follow-up information, if required or available, should all be e-mailed to Zynerva within one business day of receipt and this should be completed on a follow-up SAE form and placed with the original SAE information and kept with the appropriate section of the CRF and/or study file.

Zynerva is responsible for notifying the relevant regulatory authorities of certain events. It is the Investigator's responsibility to notify the Institutional Review Board (IRB) or Independent Ethics Committee (IEC) of all SAEs that occur at his or her site. Investigators will also be notified of all unexpected, serious, drug-related events (7/15 Day Safety Reports) that occur during the clinical trial. Each site is responsible for notifying its IRB or IEC of these additional SAEs.

13. ASSESSMENT OF PHARMACOKINETICS

13.1.1. Blood Levels of AED, CBD and THC

13.1.1.1. Blood Sample Collection

[REDACTED]

[REDACTED]

Plasma samples will be shipped to the central laboratory. The samples will be stored until the central laboratory batch ships them to the analytical laboratory chosen by the Sponsor.

An inventory of the samples shipped will accompany the package.

13.1.1.2. Sample Analysis

Plasma samples will be analyzed [REDACTED]

[REDACTED]

Plasma samples for adjunctive AEDs will be analyzed through a commercial laboratory.

All analyses will be completed to GLP standards. Results will be provided in a separate bioanalytical report.

14. STATISTICS

A Statistical Analysis Plan (SAP) will be prepared after the protocol is approved. This document will provide further details regarding the definition of analysis variables and analysis methodology to address all study objectives.

14.1. Sample Size Determination

The sample size was estimated for the primary efficacy endpoint using Power Analysis and Sample Size Software (PASS 15) (NCSS, 2017). Sample size requirements were based on a previous Phase 1/2 trial, ZYN2-CL-009, in patients with FXS and on published results in the literature with other studied treatments in this indication. [REDACTED]

14.2. Analysis Populations

The safety analysis set will include all enrolled patients who receive at least one dose of trial drug (which includes placebo run-in).

The randomized safety analysis set will include all patients who receive at least one dose of randomized trial drug. The randomized safety analysis will be the primary population for safety analyses. The treatment group assignment for this population will be the treatment actually received.

The full analysis set (FAS) will include all patients in the randomized safety analysis set who have both a baseline and a post-baseline ABC-C_{FXS} assessment. The FAS set will serve as the primary efficacy study population. The treatment group assignment for analysis will be the treatment the patient was randomized to.

The PK population will include all patients who have at least one sample collected during treatment and analyzed for determination of the CBD and THC concentrations.

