- a. Percent of patients who have $\geq 25\%$ improvement from Baseline in ABC-C_{FXS} Social Avoidance subscale score at Week 12/ET.
- b. Percent of patients who have $\geq 25\%$ improvement from Baseline in ABC-C_{FXS} Irritability subscale score at Week 12/ET.
- c. Change from Baseline in ABC-C_{FXS} Social Avoidance, Irritability, and Socially Unresponsive/Lethargic subscale scores at Weeks 4 and 8.
- d. Change from Baseline in ABC-C_{FXS}, Stereotypy, Inappropriate Speech, and Hyperactivity subscale scores at Weeks 4, 8, and 12.
- e. Change from Baseline to Weeks 4, 8, and 12 in ADAMS total score and subscale scores (Manic/Hyperactive Behavior, Depressed Mood, Social Avoidance, General Anxiety and Compulsive Behavior).
- f. CGI-I at Weeks 4 and 8.
- g. Percent of patients indicating improvement on the CGI-I (dichotomized) scale at Weeks 4, 8, and 12/ET.
- h. Response rate for patients having both $\geq 25\%$ improvement from Baseline in ABC-C_{FXS} Social Avoidance subscale score AND improved on CGI-I scale at Weeks 4, 8, and 12/ET.
- i. Response rate for patients having both $\geq 25\%$ improvement from Baseline in ABC-C_{FXS} Irritability subscale score AND improved on CGI-I scale at Weeks 4, 8, and 12/ET.
- j. Change from Baseline in CGI-S at Weeks 4, 8, and 12/ET.
- k. Change from Baseline in Family Impact PedsQLTM at Week 12/ET.

The efficacy population is defined as all patients who have taken at least one dose of double-blind study medication and have at least one post-randomization ABC-C_{FXS} assessment.

Safety Analyses:

Safety assessments will include collection of AEs including seizure assessment if applicable, physical and neurological examination, Tanner Stage assessment, 12-lead ECG, clinical laboratory assessments (hematology, chemistry, and urinalysis), vital signs, C-SSRS, MWC, PWC-20, and findings from the skin check examinations following treatment. All patients who receive at least one dose of randomized trial drug will be included in the safety analysis.

Plasma Concentrations of CBD, THC and AEDs:

Plasma concentrations for CBD, THC and concurrent AEDs will be summarized by randomized treatment group (active or placebo) and by Screening and treatment time points. Plasma may also be analyzed for CBD metabolite concentrations. [REDACTED]

Statistical Methods:

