11.3. Secondary Endpoints

- a) Percent of patients who have $\geq 25\%$ improvement from Baseline in ABC-C_{FXS} Social Avoidance subscale score at Week 12/ET.
- b) Percent of patients who have $\geq 25\%$ improvement from Baseline in ABC-C_{FXS} Irritability subscale score at Week 12/ET.
- c) Change from Baseline in ABC-C_{FXS} Social Avoidance, Irritability, and Socially Unresponsive/Lethargic subscale scores at Weeks 4 and 8.
- d) Change from Baseline in ABC-C_{FXS} Stereotypy, Inappropriate Speech, and Hyperactivity subscale scores at Weeks 4, 8, and 12.
- e) Change from Baseline to Weeks 4, 8, and 12 in ADAMS total score and subscale scores (Manic/Hyperactive Behavior, Depressed Mood, Social Avoidance, General Anxiety and Compulsive Behavior).
- f) CGI-I at Weeks 4 and 8.
- g) Percent of patients indicating improvement on the CGI-I (dichotomized) scale at Weeks 4, 8, and 12/ET.
- h) Response rate for patients having both $\geq 25\%$ improvement from Baseline in ABC-C_{FXS} Social Avoidance subscale score AND improved on CGI-I scale at Weeks 4, 8, and 12/ET.
- i) Response rate for patients having both $\geq 25\%$ improvement from Baseline in ABC-C_{FXS} Irritability subscale score AND improved on CGI-I scale at Weeks 4, 8, and 12/ET.
- j) Change from Baseline in CGI-S at Weeks 4, 8, and 12/ET.
- k) Change from Baseline in Family Impact PedsQL™ at Week 12/ET.

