14.3.3. Secondary Efficacy Analyses

All secondary endpoints including change from Baseline in ABC-C_{FXS} Social Avoidance, Irritability, Inappropriate Speech, Stereotypy and Hyperactivity subscales scores and changes from Baseline in the ADAMS total score and subscale scores, will also be analyzed using the same MMRM approach as the primary endpoint.

The statistical comparison of active versus placebo for the CGI-I at weeks 4 and 8 will be based on Wilcoxon rank sum test. The statistical comparison of active versus placebo for the CGI-S will be based on a covariate adjusted Cochran-Mantel-Haenszel (CMH) test, adjusting for the baseline score as the covariate.

A patient will be considered as “improved” on the CGI-I scale if they are rated as “1-very much improved” or “2-much improved”. All other ratings, including missing values, will be considered “not improved” (Guy 1976; Berry-Kravis et al. 2017). The response rates for the percent of patients improved using CGI-I, and for patients having both $\geq 25\%$ improvement from Baseline in ABC-C_{FXS} Social Avoidance subscale score AND improved on CGI-I scale will be compared using the chi-square test and binomial confidence intervals.

Change from Baseline in Family Impact PedsQLTM will be analyzed using ANCOVA. ANCOVA models will contain fixed effects for treatment, region and study site with Baseline value for the dependent variable of interest as a covariate.

For MMRM/ANCOVA, descriptive statistics will be presented by visit, which will include LS mean, LS standard errors, LS mean treatment difference (active-placebo) and associated 95% confidence interval (CI) and p-values for between treatment group tests.

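### For the CGI-I responder endpoints, the FAS removes dosed patients with no post-baseline ABC-C before the rule that counts missing ratings as not improved can reach them

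*Combined protocol and SAP*

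**What the plan says.** **Population.** Section 14.2 builds the full analysis set (FAS) from the randomized safety set and keeps only patients "who have both a baseline and a post-baseline ABC-C_{FXS} assessment". It then states: "The FAS set will serve as the primary efficacy study population". The synopsis has the same condition, defining the efficacy population as patients who "have taken at least one dose of double-blind study medication and have at least one post-randomization ABC-C_{FXS} assessment". The wider set is also defined in section 14.2, "The randomized safety analysis set will include all patients who receive at least one dose of randomized trial drug", but it is assigned to safety and grouped by treatment received. No other efficacy set is visible.

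**Missing ratings.** Section 14.3.3 counts CGI-I ratings of 1 or 2 as improved and adds: "All other ratings, including missing values, will be considered" not improved. Response rates "will be compared using the chi-square test and binomial confidence intervals".

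**Endpoints.** Section 11.3 g is "Percent of patients indicating improvement on the CGI-I (dichotomized) scale at Weeks 4, 8, and 12/ET". Sections 11.3 h and i require CGI-I improvement together with at least 25% improvement in ABC-C Social Avoidance or Irritability. Sections 11.3 a and b are the ABC-C-only responder endpoints; no rule for their missing values is visible.

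**Timing.** After randomization at Visit 3, the ABC-C and the CGI-I are both scheduled at Visits 4, 5 and 6/ET (Table 3; sections 7.6.19.1 and 7.6.19.4). Section 7.5 asks for every effort to complete ET procedures when a patient discontinues.

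**The concern.** The two rules pull against each other. Counting a missing rating as not improved keeps dropouts in the denominator. The FAS condition first removes those dropouts who have no post-baseline ABC-C at all. A patient rated at Week 4 and then lost counts as not improved at Week 12; a patient lost before any post-baseline ABC-C is not counted.

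Whether a patient has a post-baseline ABC-C is settled after randomization, and treatment could influence it. Conditioning on it gives up part of the protection of randomization. An MMRM of change needs a post-baseline score, so the condition is natural there. A response rate that scores missing as failure does not need one. Entry to the FAS also rests on a caregiver-completed scale, while endpoint g uses only the clinician's rating.

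At stake is the size, and possibly the nominal significance, of the secondary response-rate comparisons.

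**Working it through.** **Inputs from the documents.** 102 patients per arm, 1:1 allocation (synopsis, Statistical Methods; section 11.4). The test is chi-square (section 14.3.3).

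**The plan's own figure.** With a difference of 1.3, SD 2.8, two-sided 5% and 90% power, a two-sample t-test needs 98.46, so 99 per arm. Power at 102 per arm is 0.91. The stated 102 is consistent with this. It serves here only as the arm size.

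**Assumed inputs.** The documents give no response rates and no expected number of patients without a post-baseline ABC-C. The counts below are assumptions. Excluded patients are taken to have no CGI-I rating of 1 or 2.

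**Formulas.** With r improved and k excluded in an arm of 102:
- all-dosed rate = r/102
- FAS rate = r/(102 − k)
- ratio of FAS to all-dosed rate = 102/(102 − k), which is 1.02 for k = 2, 1.05 for k = 5 and 1.11 for k = 10.

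**Results, 38 active vs 25 placebo improved** (Pearson chi-square, no continuity correction):

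| Excluded, active/placebo | Active | Placebo | Difference (points) | p |
|---|---|---|---|---|
| none (all dosed) | 38/102 = 37.3% | 25/102 = 24.5% | 12.7 | 0.049 |
| 2/1 | 38/100 = 38.0% | 25/101 = 24.8% | 13.2 | 0.043 |
| 5/5 | 38/97 = 39.2% | 25/97 = 25.8% | 13.4 | 0.046 |
| 6/1 | 38/96 = 39.6% | 25/101 = 24.8% | 14.8 | 0.026 |
| 1/6 | 38/101 = 37.6% | 25/96 = 26.0% | 11.6 | 0.08 |

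Balanced loss of 5 per arm moves the difference by 0.7 points. An imbalance of five patients moves it up by 2.1 points (6/1) or down by 1.2 points (1/6).

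**A second assumed case, 54 vs 41 improved.** All dosed: 52.9% vs 40.2%, 12.7 points, p = 0.068. Excluding 5 active and 0 placebo: 54/97 = 55.7% vs 40.2%, 15.5 points, p = 0.029. Excluding 5 per arm: 13.4 points, p = 0.062. A result near 0.05 can therefore cross it when losses are unbalanced, and hardly moves when they are balanced.

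**The case against.** **The affected group is small.** Because the ABC-C is scheduled at ET, a child who stops for skin irritation and attends that visit stays in the FAS. The sponsor's 12-week epilepsy trial gives a rough guide to dropout. It randomized 188 (section 5.3.3), and the 171 who entered its open-label continuation study are described in section 5.3 as 98% of completers. That implies 171/0.98 ≈ 174 completers and (188 − 174)/188 ≈ 7% dropout, or about 7 of 102 per arm. Six active patients with no ABC-C at any visit, ET included, would be most of that. The guide is loose, since that continuation study was in adults with epilepsy, but the point stands: 2/1 is easier to believe than 6/1.

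**The mechanism is damped.** All patients use placebo gel in the lead-in, so some intolerance to the vehicle can show before randomization, and the application site may be moved for redness. The ABC-C and CGI-I share visits and can both be done remotely (section 19.1), so a CGI-I rating without an ABC-C should be rare. This lowers the likely size but does not remove the gap.

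**The SAP may settle it.** Section 14 defers details to a SAP that is not in the text reviewed, and calling the FAS primary does not bar a supplementary analysis. Section 14.3.3 also does not tie the responder endpoints to the FAS by name; that follows from no other efficacy set being offered. This is fair, and it makes the point one to close in the SAP.

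**Stronger readings that the documents do not support.**
- A reader might infer that the earliest treatment failures are dropped as a class. Only patients with no post-baseline ABC-C are lost, and their true outcomes are unknown; they are failures only under the plan's own scoring rule.
- A reader might infer a bias in favour of ZYN002. The direction depends on which arm loses more such patients.
- A reader might extend the conflict to 11.3 a and b. The missing-value rule is written for CGI-I, so what those endpoints have is an unstated rule.

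**Conclusion.** The inconsistency is real for 11.3 g, h and i: on the visible text, the missing-as-not-improved rule cannot reach randomized, dosed patients with no ABC-C at Visit 4, 5 or 6/ET. Under the assumed counts the shift is below 1 point when losses are few or balanced. With an imbalance of five patients it is about 1 to 3 points, in either direction. In the 38 vs 25 example with 6/1 excluded, p stays below 0.05 with both denominators; with 1/6 excluded it does not.

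Severity is minor. The endpoints are secondary and not key secondary. The primary MMRM is untouched, and the key secondary Wilcoxon test of CGI-I does not use the dichotomized rule. Section 14.7 on multiplicity is redacted, so nothing visible shows that a decision rests on these p-values. The conclusion assumes that the responder endpoints are analysed in the FAS.

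**What to change.** In sections 14.2 and 14.3.3, or in the SAP before unblinding:

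1. Analyse 11.3 g, h and i in all randomized patients with at least one dose of randomized trial drug, grouped as randomized, with a missing component counted as non-response.
2. Use every available CGI-I rating, whether or not a post-baseline ABC-C exists.
3. Apply the same population and non-response rule to 11.3 a and b. This adds a rule where none is visible.
4. Report the number of dosed patients excluded from the FAS, by arm.
5. Keep the FAS for the MMRM endpoints.

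The cost is wording only, with no new visits or data. Response rates may come out slightly lower, because the denominators include every dosed patient.
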